7.0 Data and Specimen Banking*

N/A

8.0 Sharing of Results with Subjects*

Results will not be shared

PROTOCOL TITLE: Accuracy of manual palpation vs ultrasound for spinal anesthesia in children less than 1 year of age.

9.0 Study Timelines*

- An individual study subject's participation in the study should last approximately 15-30 minutes total.
- All study subjects should be enrolled within 1 year of study start.
- The study should be completed within 2 years of study start.

10.0 Inclusion and Exclusion Criteria*

10.1 Potential subjects will be identified by reviewing the surgery schedule in Epic and will be recruited from the Surgery Unit pre-op area prior to their surgery.

10.2 *Inclusion criteria:* Patients less than 1 year of age scheduled for spinal anesthesia for elective lower abdominal, urologic, or lower extremity surgery at Nationwide Children's Hospital.

10.3 *Exclusion criteria:*
Parents unwilling for their children to undergo spinal anesthesia for surgery.
Children with known spinal anomalies including sacral dimple.
Children with coagulation abnormalities or receiving anticoagulation which precludes the use of spinal anesthesia.
Children with superficial or deep infections over the spine which precludes the use of spinal anesthesia.

11.0 Vulnerable Populations*

11.1 This study presents no more than minimal risk as it only involves ultrasound which is non-invasive, will add less than 10 minutes to the total anesthetic time, and written consent is normally not required.

12.0 Local Number of Subjects

12.1 50

13.0 Recruitment Methods

13.1 Subjects will be recruited from the surgery unit pre-op area. They will be identified by reviewing OR schedules in Epic.

14.0 Withdrawal of Subjects*

N/A

15.0 Risks to Subjects*

15.1 Although not likely, there may be a potential risk for breach of patient health information. There are no study related physical risks to study subjects associated with this study. All study related procedures are non-invasive.

15.2 Subject information will not be given to any other investigators. Subjects and their information will be closely monitored and guarded by study staff; there will be limited access to patients and their information by trained study

PROTOCOL TITLE: Accuracy of manual palpation vs ultrasound for spinal anesthesia in children less than 1 year of age.

staff; and subject information will only be shared and discussed between study staff specific to this study. Subject PHI will be stored in a locked cabinet, and will be stored and maintained in password protected computer files.

16.0 Potential Benefits to Subjects*

16.1 No direct benefit to the subject.

17.0 Data Management* and Confidentiality

17.1 A 2 by 2 contingency table with a chi-squared analysis will be performed to compare the accuracy of surface palpation versus ultrasonography. Other data including time to perform ultrasonography and level at which the conus medullaris ends will be presented as secondary outcomes in tabular format for descriptive purposes without the need for statistical comparison or analysis.

17.2 Research records will be stored in a locked cabinet and password protected computer. Only certified research personnel will be given access to identifiable subject information.

17.3 Once the data collection and analysis are complete and the study results have been published identifiers will be destroyed. Six years after research is complete, per NCH guidelines as this meets both HIPAA and OHRP regulations, all electronic files will be permanently deleted.

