1.0 Study Summary

Study Title	Assessment of the accuracy of the manual palpation of surface landmarks versus ultrasound for identification of the correct intervertebral space for spinal anesthesia in children less than 1 year of age.
Study Design	Prospective study
Primary Objective	The primary objective of the study is to compare the accuracy of manual palpation of surface landmarks versus ultrasonography for identification of the appropriate interspace for lumbar puncture and spinal anesthesia in infants less than 1 year of age.
Secondary Objective(s)	The secondary objective is to assess the level of the conus medullaris in infants in the sitting and lateral position.
Research Intervention(s)/ Investigational Agent(s)	Ultrasound
IND/IDE #	N/A
Study Population	Main OR surgical patients
Sample Size	50
Study Duration for individual participants	Less than 30 minutes total.
Study Specific Abbreviations/ Definitions	N/A

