2.0 Objectives

- 2.1 The primary objective of the study is to compare the accuracy of manual palpation of surface landmarks versus ultrasonography for identification of the appropriate interspace for lumbar puncture and spinal anesthesia in infants less than 1 year of age.
- 2.2 The secondary objective is to assess the level of the conus medullaris in infants in the lateral position and also in the sitting position.
- 2.3 The hypothesis is that ultrasonography will be more accurate than the traditional method of palpation of surface landmarks in the identification of the appropriate interspace for lumbar puncture and spinal anesthesia in children less than 1 year of age.

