3.0 Background

- 3.1 Spinal anesthesia may be used instead of general anesthesia in children for lower abdominal surgical procedures. The conus medullaris ends at L3-L4 in children less than 1 year of age and therefore the L3-4 or L4-5 interspace is

PROTOCOL TITLE: Accuracy of manual palpation vs ultrasound for spinal anesthesia in children less than 1 year of age.

suggested as the optimal site for lumbar puncture for spinal anesthesia. Manual palpation is commonly performed to identify the correct intervertebral space for spinal anesthesia. Studies in adults and children have shown that manual palpation can be inaccurate in up to 30% of cases.¹⁻³ Traumatic needle placement or the administration of a concentrated local anesthetic agent into the spinal cord can lead to serious morbidity including neurologic damage and even paraplegia.^{2,4} Ultrasonography may be used to assess the intervertebral space prior to spinal anesthesia in adults especially in difficult cases and in children to locate the tip of epidural catheter. Introduction of the ultrasound for assessment of the correct intervertebral space for spinal anesthesia may decrease the number of attempts and the possibility the incidence of serious adverse effects.

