4.0 Study Endpoints

- 4.1 The accuracy of manual palpation of surface landmarks for identification of the appropriate interspace (L3-4/L4-5) for lumbar puncture and spinal anesthesia.
- 4.2 The level of the conus medullaris lateral and sitting.

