6.0 Procedures Involved*

- 6.1 Anesthetic management will not vary from the standard technique and will be at the discretion of the anesthesia team. The clinical anesthesia provider (fellow or attending) who will be performing spinal anesthesia will mark the interspace for spinal anesthesia with a marking pen. The study team will record the providers years of experience performing spinal anesthesia. The research anesthesiologist performing the ultrasound will confirm whether or not the appropriate interspace (L3-4/L4-5) has been identified. Also, the interspace where the conus medullaris ends will be identified in the sitting position. Spinal anesthesia will be performed at the space confirmed by ultrasound using our standard clinical care.

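### The planned 2 by 2 chi-squared test does not fit paired readings on the same 50 infants, and its large-sample p-value is unreliable when palpation errors are few

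*Combined protocol and SAP*

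**What the plan says.** The only inferential analysis is in section 17.1: "A 2 by 2 contingency table with a chi-squared analysis will be performed to compare the accuracy of surface palpation versus ultrasonography". Everything else there is descriptive. The section does not say how the rows and columns of the table are defined. It gives no significance level, sidedness or continuity correction, and mentions no paired or exact method.

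Section 6.1 describes one cohort with no allocation to groups. In each infant the provider "will mark the interspace for spinal anesthesia with a marking pen", and then: "The research anesthesiologist performing the ultrasound will confirm whether or not the appropriate interspace (L3-4/L4-5) has been identified". The Study Summary gives "Sample Size 50", repeated in section 12.1 without justification.

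Endpoint 4.1 concerns palpation alone: "The accuracy of manual palpation of surface landmarks for identification of the appropriate interspace (L3-4/L4-5) for lumbar puncture and spinal anesthesia". No accuracy endpoint for ultrasound is listed. The hypothesis in section 2.3 is nevertheless comparative: "The hypothesis is that ultrasonography will be more accurate than the traditional method of palpation of surface landmarks". The only error rate in the documents is in section 3.1, where "manual palpation can be inaccurate in up to 30% of cases".

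**The concern.** There are two separate defects.

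First, a chi-squared test on a table of method by correct/incorrect assumes that all entries are independent. Here 50 infants each contribute two entries, so the table holds 100 entries from 50 independent units. The test does not match the design.

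Second, the documents describe no standard other than ultrasound for deciding whether the marked interspace is right. Ultrasound is therefore scored correct every time, and one cell of the table is fixed at zero. When palpation errors are few, the expected counts are too small for the large-sample chi-squared p-value to be trusted.

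At stake is the p-value attached to the study's single hypothesis. With a handful of palpation errors, the conclusion could depend on which version of an unspecified test the analyst happens to run.

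**Working it through.** **Inputs.** n = 50 infants (sections 1.0 and 12.1). Ultrasound errors = 0 of 50, because ultrasound decides whether the mark is right (section 6.1). k = palpation errors. Assumed, since the plan does not state them: two-sided 0.05, and no continuity correction unless noted. The plan gives no power, effect size or threshold, so there is no stated figure to reproduce.

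**Expected counts.** The table has rows (50−k, k) for palpation and (50, 0) for ultrasound. The expected count in each error cell is 50 × k/100 = k/2. At k=4 this is 2.0, and it reaches 5 only at k=10.

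**Test statistics.**
- Unpaired Pearson, uncorrected: 100 × (50k)² / [50 × 50 × k × (100−k)] = 100k/(100−k). At k=4, 400/96 = 4.17; at k=5, 500/95 = 5.26; at k=6, 600/94 = 6.38.
- Paired McNemar, uncorrected: (k−0)²/(k+0) = k.
- Paired McNemar, exact two-sided: p = 2 × 0.5^k.

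| k | Pearson, uncorrected | Yates | Fisher | McNemar, uncorrected | McNemar, exact |
|---|---|---|---|---|---|
| 3 | 0.079 | 0.241 | 0.242 | 0.083 | 0.250 |
| 4 | 0.041 | 0.126 | 0.118 | 0.0455 | 0.125 |
| 5 | 0.022 | 0.067 | 0.056 | 0.025 | 0.0625 |
| 6 | 0.012 | 0.035 | 0.027 | 0.014 | 0.031 |

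**What causes the gap.** Uncorrected Pearson is first significant at 4 errors and exact McNemar at 6. Uncorrected McNemar, which is paired, also starts at 4. Yates and Fisher, which are unpaired, also start at 6. At k=4, allowing for pairing moves the uncorrected statistic only from 4.17 to 4.00. The gap is therefore the large-sample approximation in sparse cells.

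**Sidedness.** At one-sided 0.05 the thresholds would be 3 errors (0.079/2 = 0.039) and 5 errors (0.5^5 = 0.031), so the gap has the same width.

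**How often it could matter.** The tests disagree at k=4 or 5. With k binomial(50, q), P(k=4 or 5) = P(k≥4) − P(k≥6):

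| True palpation error q | P(4 or 5 errors) |
|---|---|
| 8% (assumed) | 0.367 |
| 10% (assumed) | 0.7497 − 0.3839 = 0.366 |
| 15% (assumed) | 0.9540 − 0.7806 = 0.173 |
| 20% (assumed) | 0.9943 − 0.9520 = 0.042 |
| 30% (section 3.1) | 1.0000 − 0.9993 = 0.0007 |

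At 15 of 50 errors (30%), Pearson, Yates, Fisher and exact McNemar all give p<0.0001.

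**What the design can estimate.** Exact binomial 95% CIs for the palpation error rate are 2.2% to 19.2% for 4/50, 4.5% to 24.3% for 6/50, and 17.9% to 44.6% for 15/50. The last corresponds to accuracy of 70%, with CI 55.4% to 82.1%.

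**The case against.** The strongest reply is that the choice of test hardly matters here. At the one error rate that the documents cite, every candidate test gives the same answer. The 4-error threshold also depends on reading the plan as an uncorrected test: with Yates correction the planned chi-squared test needs 6 errors, as exact McNemar does. Both statements are correct and limit the size of the point. They do not remove it. Section 3.1 gives 30% as an upper figure, so lower rates remain possible, and section 17.1 leaves open which version will be run.

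The sponsor might also say that a paired table was intended. Section 17.1 does not say so. An ordinary chi-squared test on a palpation-by-ultrasound cross-tabulation would be undefined, because the ultrasound-incorrect margin is empty. Uncorrected McNemar would still carry the sparse-cell problem (p=0.0455 at k=4).

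Two stronger readings are tempting, and the documents support neither. A reader might infer that ignoring the pairing is what lowers the threshold from 6 errors to 4; the comparison of tests above shows otherwise. A reader might also infer that ignoring the pairing inflates the false-positive rate, or costs power, by some definite amount. Any such figure needs ultrasound to be scored against an independent standard and needs a within-infant correlation. The plan has neither, and with ultrasound errors fixed at zero that correlation is undefined. Even the direction of the effect would depend on the correlation assumed.

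**Conclusion.** The concern holds in this form. The sole planned test assumes independent groups where the design gives 50 pairs. Because ultrasound is its own reference, the error cells are also sparse whenever there are fewer than 10 palpation errors. Under two-sided 0.05 without continuity correction, the planned test would call 4 or 5 errors significant where exact McNemar, Fisher and Yates would not.

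The practical effect is confined to low error rates. The conclusion would be open to this difference in about 37% of studies if true palpation error is 8-10%, a range assumed here, and in fewer than 0.1% at 30%. The documents do not support saying that the study's conclusion would usually be wrong.

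An exact paired test alone would not repair the analysis. With ultrasound as the reference, all disagreement must run one way, so the test would compare palpation with a method that cannot be scored wrong. What the design does support is an estimate of palpation accuracy.

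**What to change.** In section 17.1, replace the chi-squared sentence with a statement that palpation accuracy against ultrasound will be reported as a proportion of the 50 infants with an exact binomial 95% CI, and that no two-method test will be made while ultrasound is the reference. This matches endpoint 4.1. The comparative wording in sections 2.1 and 2.3 should then be brought into line.

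Keep a two-method comparison only if ultrasound is scored against a separate standard. In that case, cross-tabulate palpation correct/incorrect by ultrasound correct/incorrect within infant (50 pairs), use the exact McNemar test, state alpha and sidedness, and give a paired 95% CI for the difference.

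Under the current design the change to 17.1 is a sentence or two and needs no extra data or subjects. The cost is that there is no p-value for palpation versus ultrasound, and that the evidence looks less favourable to ultrasound when palpation errors are few. A separate reference standard would be a larger change, because the documents describe none.

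### Section 17.1 specifies no within-infant summary and no interval for conus level, although lateral and sitting levels in one cohort are the secondary endpoint

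*Combined protocol and SAP*

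**What the plan says.** Section 2.2 sets the secondary objective: to "assess the level of the conus medullaris in infants in the lateral position and also in the sitting position". Section 1.0 says the same in other words. Section 4.2 lists the matching endpoint: "The level of the conus medullaris lateral and sitting". Sections 1.0 and 12.1 give 50 subjects. No infant is allocated to one position or the other, so the natural reading is two levels per infant.

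The only analysis text is in 17.1. It covers "Other data including time to perform ultrasonography and level at which the conus medullaris ends", and these are to be "presented as secondary outcomes in tabular format for descriptive purposes without the need for statistical comparison or analysis". It does not mention position, pairing, change of level, a proportion or an interval, and no other section does so for this endpoint.

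Section 6.1 describes one conus reading: "the interspace where the conus medullaris ends will be identified in the sitting position". It describes no lateral reading.

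**The concern.** Naming two positions as the only secondary objective has little purpose unless the report shows how the level relates to position. In a single cohort that information lies in the pairs: which infants have a different level in the second position, and in which direction. A plan that asks only for a table permits one frequency column per position, and two such columns discard the pairs. Similar columns could then be read as showing that position makes no difference, although they are compatible with a great deal of individual movement in both directions.

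The second issue is precision. Section 3.1 relates the end of the conus to the suggested puncture interspaces and names serious neurologic harm. Readers will therefore look at how many infants have the conus at or below L3-4. A bare count from 50 infants, especially a count of zero, is easily taken as firmer than it is.

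**Working it through.** **Inputs.** From the documents: n = 50 (1.0, 12.1), two positions (2.2, 4.2), one cohort. The plan states no figure for the conus endpoint, and the sample size carries no alpha, power or precision target, so there is no figure to reproduce. Assumed for illustration: both readings taken in all 50 infants, and the counts used below.

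**Step 1: two levels.** Let s and l be the numbers at the lower level when sitting and lateral. Given only these totals, the number of infants who change lies between |s − l| and min(s, 50 − l) + min(l, 50 − s).

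- s = 10, l = 10: from 0 to 10 + 10 = 20.
- s = 10, l = 15: from 5 to 10 + 15 = 25.
- s = 25, l = 25: from 0 to 25 + 25 = 50.

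**Step 2: three levels.** Take L1-2/L2-3/L3-4 totals of 20/25/5 lateral and 18/26/6 sitting.

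- Fewest changers: the most that can stay put is min(20,18) + min(25,26) + min(5,6) = 18 + 25 + 5 = 48, so at least 2 change.
- Most changers: at L2-3, 25 + 26 − 50 = 1 infant must stay; the other levels force none. So at most 49 change.
- Caudal moves, fewest: L1-2 falls from 20 to 18, and an infant leaving it can only move caudally, so at least 2.
- Caudal moves, most: 20 from L1-2, plus at most 6 from L2-3 into L3-4, so 26.

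Both extremes are attained by tables with exactly these totals:

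| Lateral level | Sitting L1-2 / L2-3 / L3-4, fewest changers | Sitting L1-2 / L2-3 / L3-4, most changers |
|---|---|---|
| L1-2 (20) | 18 / 1 / 1 | 0 / 20 / 0 |
| L2-3 (25) | 0 / 25 / 0 | 18 / 1 / 6 |
| L3-4 (5) | 0 / 0 / 5 | 0 / 5 / 0 |
| Column totals | 18 / 26 / 6 | 18 / 26 / 6 |
| Changers | 2 (2 caudal, 0 cranial) | 49 (26 caudal, 23 cranial) |

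If moves are limited to one level, the minimum rises to 3 (2 from L1-2 to L2-3, 1 from L2-3 to L3-4). The maxima stay at 49 and 26, because the right-hand table uses one-level moves only.

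**Step 3: precision.** The Clopper-Pearson 95% limits for x of 50 are the 2.5% point of Beta(x, 51 − x) and the 97.5% point of Beta(x + 1, 50 − x). For x = 0 the upper limit is 1 − 0.025^(1/50) = 7.1%.

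| Count | Exact 95% interval |
|---|---|
| 0/50 | 0 to 7.1% |
| 5/50 | 3.3 to 21.8% |
| 10/50 | 10.0 to 33.7% |
| 25/50 | 35.5 to 64.5% |

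These apply equally to a proportion changing level and to a proportion at or below L3-4. By symmetry, 50/50 gives 92.9 to 100%.

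**Step 4: which summaries the protocol supports.** If 2.2 and 4.2 are followed, each infant has two readings and every paired summary is available. If 6.1 is followed as written, each infant has one sitting reading, and only the sitting proportion with its interval is available. Section 17.1 does not settle the matter, because it does not mention position.

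**The case against.** The strongest reply is that nothing in 17.1 is wrong. The objective is to assess the level in each position, not to compare positions. The only hypothesis is "The hypothesis is that ultrasonography will be more accurate than the traditional method of palpation of surface landmarks", and the only planned test serves that question: "A 2 by 2 contingency table with a chi-squared analysis will be performed to compare the accuracy of surface palpation versus ultrasonography". Descriptive tabulation of a secondary outcome is consistent with an objective to assess. This stands as far as it goes: the documents state no aim to test or estimate a change with position, so the point is an improvement in method and not a contradiction.

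Three stronger readings are tempting, and the documents do not support them.

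- A reader might infer that 17.1 forbids comparison. It calls comparison unnecessary, which is not a prohibition.
- A reader might infer that the data will be reduced to two unlinked columns. No layout is given, and a per-infant cross-table is also tabular and descriptive. The range of 2 to 49 holds only if separate columns are used.
- A reader might infer that such columns could not show whether the level changes at all. Unequal columns do show some change: in the example, at least 2 infants. What they leave open is how many.

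The upper end of 49 is a mathematical bound. It needs near-balanced opposite shifts across almost the whole cohort and is not a forecast.

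It is also fair to say that the share at or below L3-4 is not a listed endpoint. Section 3.1 places the end of the conus at L3-L4 in this age group, so a count near zero may not be the likely result. The need for an interval does not depend on that: at 25/50 it runs from 35.5 to 64.5%. A reader could calculate an interval for a marginal count from a published table, but could not recover the pairs from separate columns.

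The most substantial objection is that the paired data are not secured, because 6.1 describes a sitting reading only. It stands, and it limits what the change to 17.1 can achieve alone.

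**Conclusion.** The point holds as a cheap improvement that should be made. For a secondary endpoint named in two positions, 17.1 specifies neither a within-infant summary nor an interval. Under a compliant layout of separate columns, the number of infants changing level could be unidentified over a range as wide as 2 to 49 of 50. Under any layout without intervals, a zero count would conceal an upper limit of 7.1%.

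This rests on three assumptions: both readings are taken in all 50 infants, the illustrative counts are hypothetical, and the two positions are meant to be observed in the same infant, which the documents imply but do not state. Fewer complete pairs would widen the intervals. The primary comparison is unaffected.

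A reader might infer that a test of position is needed. It is not, since no position hypothesis exists. If all shifts went one way, an exact sign test would need 6 changers to fall below 0.05 (2 × 0.5^6 = 0.031, against 2 × 0.5^5 = 0.0625 for 5). Estimates with intervals suit the descriptive aim.

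**What to change.** In 17.1, separate the conus endpoint from the other descriptive data and specify:

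1. a per-infant cross-tabulation of lateral by sitting level;
2. the number and proportion of infants whose level moves caudally, and the number and proportion whose level moves cranially, each with an exact (Clopper-Pearson) 95% confidence interval;
3. for each position, the proportion with the conus at or below L3-4, with an exact 95% confidence interval.

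No hypothesis test need be added.

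Items 1 and 2 and the lateral part of item 3 require a lateral reading. Sections 2.2, 4.2, 6.1 and 17.1 must therefore be reconciled so that objective, endpoint, procedure and analysis name the same readings. The sitting part of item 3 can be reported either way.

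The cost is two or three sentences in 17.1 and a few minutes of analysis. The analysis uses no data beyond the two readings that 4.2 names, though 6.1 does not yet provide for the lateral one. The small downside is that the report will show wide intervals. Settling the summaries before the data are seen also prevents a choice driven by the results.
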